Absorbed blood in gauze: measure weight of the gauze before the operation then calculate the difference after the operation.

Absorbed amount of blood using inhalator: blood collected in the inhalator bottle will be moved to the 50cc syringe then the amount of blood will be measured. If saline is used for wash out operation region during the operation, that amount will be omitted.

- ② Operation time
- ③ Transfusion volume

(2) Pre- and Post- operation management

- i. Within a month from the date of operation: A laboratory test (CBC, admission panel, CRP, triglyceride, amylase, PT, aPTT), age, medical history, ASA classification, weight, height.
- ii. 1 day before operation: bowel preparation (empty stomach and enema): use of a laxative before operation (Mg. citrate powder intake, suppository bisacodyl 10mg) and suppository glycerin enema and bisacodyl 10mg on the day of operation.
- iii. low molecular weight heparin (LMWH): to prevent DVT, hypodermic medication of 20mg 1 time/ 1day may possible after 2 ~3 days post operatively.

(3) Post-operative evaluation

- PCA (patient controlled analgesia): includes Morphin and fentanyl. When need additional pain control, Nalbuphin (IM) or Fentanyl patch will be used
- 2 From POD 1 to 4, VAS pain score will be measured daily.
- 3 Gas out, day of starting liquid diet will be recorded
- ④ Complications: Within the follow-up period, from the end of operation to 2-3 weeks after discharge, patients will be monitored to check for complications and mortality before POD 30. Complications will be measured by Clavien-Dindo classification. Any reasons for re-admission through an out-patient clinic or emergency during the followup period will separately be recorded.

(4) Laboratory test

i. POD 2, 4: Blood test (CBC, admission panel, CRP, triglyceride, amylase)

ii. POD 2: Amylase and triglyceride test in the drain. Measurement of drainage by 1-3 days after surgery

iii. Cytokines Test:

- Serum IL-6, IL-10: Obtain peripheral blood in 5ml bottle of EDTA bottle : just after the induction of the anesthetia, 2-3 hours after the end of the operation, the 2nd post-operative day, and the 4th post-operative day.
- EDTA bottle is centrifuged at 3000 rpm for 15 minutes as soon as possible after collection. It is divided into 200ul each, and then cytokine assay is asked to clinical research laboratory. On holidays when it is difficult to conduct the test, it is centrifuged, stored at -80 °C and analyzed at the day available.

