item Pre-Op (Baseline			Intra-		PC	DD (Post	Operativ	1st outpatient visit after discharge	End of study/ Early termination		
	(Baseline)	abdomen	Ор	2-3hr	#1	#2	#3	#4	Discharge		
Informed consent ¹	✓										
Selection/exclusion criteria	√										
Demographic information	✓										
History, ASA	✓										✓
Physical examination, weight	*										√
Random assignment		✓									
Lab (cbc, admission panel, amylase, CRP², triglyceride³)	*					*		✓		(✔)	
Blood cytokine ⁴		✓		*		1		1			
JP drain amount					1	1	1				
JP drain TG, amylase						1					
ICG concentration ⁵			✓								
Operation ⁶											
Blood volume			✓								✓
Operation time			✓								✓
Amount of blood transfusion			✓								✓
Surgical information			✓								✓
Analgesic medication (excluding PCA)					√	✓	*	√			
VAS pain score	*				1	✓	1	1			
Gas out day									✓		
Soft diet starting date									✓		
EGD, EUS,CT	✓										
Hospital stay count									✓		✓
Pathologic result confirmation	1								✓	*	
Adverse events ⁷			✓	✓	*	√	✓	✓	*	1	✓
Follow-up visit		_								1	

All procedures, including selection / exclusion criteria, may be initiated after voluntary written consent has been obtained from the subject. If surgery is not performed within thirty days after obtaining the consent form, the procedures for rehabilitation shall be carried out.

CRP was further examined within 2 days before surgery

Triglyceride is examined by the researcher's option on the first outpatient visit after discharge

After patient anesthesia in the surgical field, blood is drawn through the A-line.

Only for Seoul National University Hospital

Surgery is performed according to standard surgical guidelines.
 Adverse events are evaluated up to POD # 30.

4-1) Baseline before surgery

- 1) Subject consent form
- 2) Demographic information
- 3) Detailed medical history
- 4) Significant medication or operation history
- 5) Physical examincation
- 6) Laboratory test: CBC, PT, aPTT, BUN, Triglyceride, Albumin, Total bilirubin, Creatinine, CRP, Amylase, use the test results within 30 days before surgery
- 7) Concomitant medication (including drugs within the past week)
- 8) EGD, EUS, CT use test results within 2 months from the scheduled date of surgery.
- 9) Measure VAS score on the day before surgery.

4-2) operation day

- 1) Randomization: prior to surgery.

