- 2) Operation method: Lymph node dissection range (D1+) and removed lymph node area, mating method, etc. are recorded; and the ablation range is left as a photograph.
- 3) Volume of blood loss
- 4) Operation time
- 5) Volume of blood transfusion
- 6) Cytokine test: as described in 11-1)-(4)
- 7) ICG measure: as described in 11-1)-(5)
- 8) Adverse reaction

4-3) POD 1 ~ discharge date

- 1) Amount of drainage: measured in 24 hour unit
- 2) Number of lymph nodes removed
- 3) Amount of blood transfusion
- 4) Adverse reaction
- 5) Laboratory test (POD 2, 4): serum CBC, admission panel, CRP, triglyceride, amylase, IL-6 and IL-10
- 6) Triglyceride and amylase from JP drain (POD 2)
- 7) Date of gas out and initiation of soft diet
- 8) Complications

4-4) Follow-up: first outpatient visit after discharge (3-4 weeks after surgery)

- 1) Adverse reaction
- 2) Complications
- 3) Re-admission or emergency visit record and reason

4-5) unscheduled evaluation and early termination:

- If an evaluation of the subject is performed at an unscheduled point of time, record the evaluation items such as adverse reactions, dropouts, clinical measurement results, and medical treatment.
- For those patients who have dropped out, the evaluation items should be measured at the time of withdrawal.

5) Differentiation from existing treatments and research

Many of the existing studies comparing energy-based devices have been performed in laboratories; so there has been a limit to assessing the effects of surgery on patients. The purpose of this study was to evaluate the effect of each surgical instrument on the patients in stomach cancer surgery, especially for lymphadenectomy and hemostasis.

6) Benefits and risks of the subject

The energy-based devices used in this study are the devices commonly used in stomach cancer surgery with the approval of the Ministry of Food and Drug Safety. The side effects and risks that may occur in this study are expected not to go beyond the range of complications that are expected to occur in stomach cancer operation, not due to the malfunction of the energy-based resection mechanism. Thus, the additional risk of participating in the study by the study participants does not outweigh the risks in general gastric cancer surgery. On the other hand, if energy-based resection devices have different effects on the subjects of clinical studies, it can provide a basis for surgeons to select surgical instruments used for gastric surgery.

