8) Standards, evaluation methods and reporting methods for safety including side effects

In this study, we will evaluate the following postoperative complication, this is not different from the complications that usually occur in stomach cancer surgery. Evaluation of complications and confirmation will be performed according to the following items and will be graded according to the Clavien-Dindo classification. The incidence of complications among the groups will be compared through crossover analysis.

- 1) Wound infection: It refers to the case where additional wounding treatment is required to wound site due to seroma, hematoma, wound infection, wound dehiscence and wound evisceration.
- 2) Fluid collection / abscess: A case of abdominal abscess confirmed by abdominal ultrasonography or computed tomography of the abdomen.
- 3) Intra-abdominal bleeding
- 4) Intraluminal bleeding
- 5) Intestinal obstruction: Refers to a case where there is a suspicion of mechanical intestinal obstruction or a suspicion of intestinal obstruction in the absence of gas passage.
- 6) Ileus: Refers to the cases of vomiting during the course of the operation after the operation or difficulty in the progress of the meal, and the presence of paralytic obstruction in the abdominal plain radiograph.
- 7) Stenosis: Upper endoscopy or upper gastrointestinal stenosis refers to the case with anastomotic stenosis.
- 8) Leakage: Case where the intestinal contents are discharged into the drain tube or leaked on examination of the upper gastrointestinal tract.
- 9) Fistula: Refers to the case identified on the fistulogram.
- 10) Pancreatitis: A case in which the serum amylase level was significantly (150 or more) elevated due to symptoms indicating pancreatitis.
- 11) Pulmonary complications: refers to atelectasis, pleural effusion, empyema, pneumonia, pneumothorax
- 12) Urinary tract infection: refers to cases in which symptoms such as frequency of urination, nocturia, urination difficulty, or urinalysis show a significant increase in WBC
- 13) Renal dysfunction: Serum Creatinine > 1.4 mg/dL (EMR reference value)
- 14) Hepatic dysfunction: GOT, GPT > 100 IU/L
- 15) Cardiac: Clinically diagnosed as heart failure or myocardiac infarction based on symptoms and signs such as pleural effusion, hypotension, chest pain, elevated cardiac enzyme, and echocardiography

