- 16) Endocrine: Diabetic ketoacidosis, hyperglycemic hyperosmolar state, Addison's disease, hypothyroidism, etc. Clinically diagnosed
- 17) Stasis: Refers to the case where food is obstructed to pass through the anastomosis, even though there is no evidence of intestinal obstruction, stenosis, leakage, or peritonitis.

- 18) Pancreatic leakage: A case when the amylase level of the drain tube 3 days or more after surgery exceeds 540 U/L, which is three times the normal maximum value of 180 U/L of the normal blood test (1, 3, Check on day 5).
- 19) Chylous ascites: Suspected when the color of a clear white fluid is found with the naked eye, and JP diagnoses that triglyceride is 110 mg/dL.
- 20) Deep Vein Thrombosis
- 21) Central venous infections

9) Evaluation standards, evaluation methods and analysis methods (statistical analysis methods, etc.)

- (1) Primary endpoint: Two days after surgery, serum CRP
- ; Student's t test or ANOVA test was performed by using the mean of CRP value on the second day between the three groups.
- (2) Secondary endpoint:
- Blood loss during operation (ml), amount of blood transfusion (pint); Output-input (ml). Gauze measures the total weight of gauze used during surgery and calculates the difference from the gauze weight measured before surgery. Inhalation volume is calculated by subtracting the amount of 0.9% physiological saline solution applied to the surgical site from the total inhalation volume.
- Serum IL-6, IL-10

Serum IL-6 and IL-10 levels were measured at baseline immediately after general anesthesia and insertion of the trocar. The mean value of serum IL-6 and IL-10 levels 2-3 hours after the operation, the 2nd postoperative day, and the 4th postoperative day are compared by Student's t test or ANOVA test.

- Amount of remaining ICG: Total amount of the remaining ICG will be calculated by the mean value of concentration of the ICG measuring 3 sets for each patient multiplied by 500 (ml) (600 or 700 ml for corresponding cases), and the mean value of the amount of ICG will be compared between each group using t test.

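### Pancreatic leakage is defined by drain amylase at day 3 or later, but drain amylase is scheduled on POD 2 only

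*Combined protocol and SAP*

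**What the plan says.** - **Definition.** Section 11, 8) lists 21 complications and says "Evaluation of complications and confirmation will be performed according to the following items". Item 18, pancreatic leakage, is "A case when the amylase level of the drain tube 3 days or more after surgery exceeds 540 U/L". The threshold is explained as three times a normal maximum of 180 U/L, and a bracket gives check days: "1, 3, Check on day 5".
- **Sampling.** Section 11, 1)(4) has "POD 2: Amylase and triglyceride test in the drain". In the section 11, 4) schedule table, the row "JP drain TG, amylase" has one tick, under POD #2. The visit list in 4-3), item 6, also gives POD 2. The POD 4 tests in 1)(4) and 4-3) are blood tests.
- **Unscheduled tests.** Section 11, 4-5): "If an evaluation of the subject is performed at an unscheduled point of time, record the evaluation items".
- **Endpoints.** Section 11, 4)(2) lists the drain concentrations of triglyceride and amylase as a secondary endpoint in their own right, apart from 30-day complications.
- **Analysis.** Section 11, 9)(2) compares amylase (fluid not named) and triglyceride in serum and ascites at POD 4. For complications it applies a chi-square test to overall frequency and to Grade IIIa, and compares a total index.
- **Drain volume.** Section 11, 1)(4) has "Measurement of drainage by 1-3 days after surgery", and the table ticks POD 1, 2 and 3. Section 4-3), which runs from POD 1 to discharge, lists drainage in 24-hour units.

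**The concern.** Item 18 is a laboratory definition. It can be met only if drain fluid is tested on a qualifying day, and the schedule contains no such test.

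Leakage is a relevant safety comparison here, because section 9, 1)(2) v lists the separation of duodenum from pancreas among the steps done with the assigned device. If the schedule governs, a leak is documented only when someone orders an extra sample. Section 11, 2) describes a single-blind trial in which the practitioner knows the allocation, so that decision could be influenced by the arm.

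Two hospitals enrol (section 10, 3)). One that worked from item 18 and one that worked from the schedule would ascertain leakage differently. Stratifying randomization by institute balances such a centre difference across arms. It does not address unblinded testing decisions within a centre.

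**Working it through.** **Threshold.** 3 × 180 = 540 U/L, which agrees with item 18. The threshold is internally consistent; the conflict is about days.

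**Drain-amylase days, by source**

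| Source (section 11) | Days |
|---|---|
| 1)(4) Laboratory test | 2 |
| 4) schedule table | 2 |
| 4-3) visit list | 2 |
| 8) item 18, named checks | 1, 3, 5 |
| 8) item 18, qualifying days | 3 or later |

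**Overlaps**

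1. Schedule {2} with qualifying days {3 or later}: none. Scheduled samples per patient that can establish leakage: 0 of 1.
2. Schedule {2} with named checks {1, 3, 5}: none, so 0 of 3 named checks are scheduled.
3. Named checks {1, 3, 5} with qualifying days {3 or later}: {3, 5}, so 2 of 3 named checks could meet the definition.

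**Does the garbled bracket matter?** No. Result 1 uses only the day-3-or-later condition. If the bracket is read as serum test days instead, the serum days {2, 4} also share nothing with {1, 3, 5}.

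**Could a POD 4 sample fill the gap?** Day 4 is late enough to qualify, although it is not a named check day. Section 9)(2) analyses ascites triglyceride at POD 4, which implies a peritoneal or drain fluid sample, and it leaves the amylase fluid open. But sections 1)(4) and 4-3) describe the POD 4 amylase as a blood test, and the table has no drain-fluid tick that day. So 9)(2) does not schedule a qualifying sample. It is one more passage that disagrees on the sampling day.

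**Is an unscheduled sample required?** No. Section 4-5) says what to record if an extra evaluation takes place; it does not call for one.

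**Share of the endpoint.** Leakage is 1 of 21 listed complications. No separate test of leakage is specified. It enters the overall complication frequency, the Grade IIIa comparison and the total index.

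**Severity category.** Read literally, a test on Grade IIIa omits IIIb, IV and V. Those grades still count in the overall frequency and the index.

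**The case against.** **The POD 2 sample has its own purpose.** This is true. It serves the drain-amylase concentration endpoint in section 11, 4)(2) and is taken on the same day in every arm, so a uniform comparison of drain amylase exists whatever happens to item 18. It still cannot establish leakage as item 18 defines it.

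**Sites may simply follow item 18.** Its check days are stated without reference to suspicion or arm. If every site samples on them, testing is not discretionary and the bias argument falls away. This stands as a condition: the argument applies only where the schedule is followed instead. Nothing in the documents shows which text the sites use, or that the two hospitals differ.

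**Stronger readings that a reader might infer.**

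- *That no drain measurement is planned by day 5.* Section 4-3) lists daily drainage through to discharge, so this is not supported. The documents disagree on drain-volume days, which is a smaller matter.
- *That late complications fall outside follow-up because the outpatient visit can come before POD 30.* The plan states a 30-day window, has an end-of-study adverse-event check separate from that visit, and records readmissions and emergency visits within 30 days. No finding is made on this.

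**Grade IIIa may have lost a phrase in translation.** Quite possibly. Confirming the intended category is enough.

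**Conclusion.** The plan contradicts itself. Three operational texts schedule drain amylase on POD 2, and the leakage definition needs day 3 or later. Under the schedule as written, 0 scheduled drain-amylase samples per patient can meet the definition.

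The reach is limited to one of 21 complications in a secondary safety endpoint. The POD 2 CRP comparison and the target of 189 patients do not depend on it. It should be corrected, but it does not threaten the main result.

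A reader might infer that leakage is certain to be undercounted, or that one device will be favoured. The documents do not support either. They give no leak rate and no testing practice, and item 18's own check days may be in use. What can be said is conditional: if the schedule is followed, detection rests on unscheduled sampling by staff aware of the device, and comparability between arms cannot be assumed.

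**What to change.** 1. Reconcile section 11, 1)(4), the schedule table, 4-3), 8) item 18 and 9)(2), so that the leakage definition, the drain-fluid sampling day or days and the analysis day agree in all arms. Name the fluid for the POD 4 amylase. Which days and which threshold apply is for the investigators; this review does not choose them.
2. Patients have already been treated, since 9)(2) describes a device change during the study. For them, report by arm how many had a drain amylase at day 3 or later, and whether it was routine or prompted by suspicion.
3. Align the drain-volume days between 1)(4), the table and 4-3).
4. In 9)(2), state the severity category as Grade IIIa or higher, or confirm that another category is meant.

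Items 1, 3 and 4 are wording. The analysis wording could go into the SAP that section 9-1) promises before database lock. Item 2 needs a chart review of drain-amylase dates. If the reconciled text adds a sampling day, the cost is one drain test per added day for each patient still to be enrolled. The sample size does not change.

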According to our preliminary results, advanced bipolar electrocautery in laparoscopic gastrectomy is expected to lower the peritoneal and systemic inflammatory response, which is reflected in serum CRP 2 days after the surgery, compared to the ultrasonic shears or the hybrid device. Hybrid device are expected to produce results similar to USA when considering the operating feature and heat generated; however, there is no previous study with hybrid device. We intend to conduct exploratory data collection and comparison with hybrid device.

The aim of this study was to evaluate the effects of energy-based shear devices used in gastric surgery on patients including postoperative inflammation.

9. Code name of the test drug, general name of the main ingredient, drug substance and its amount, dosage form, etc.

Authorization	A35025.01 (2)
Number (Rate)	
Product	HARMONIC® HD 1000i Shears, HARHD20 & HARHD36
Feature	curved shears, 36cm shaft length

A device used for the incision or coagulation of soft tissue in the surgery of general surgery, plastic surgery, pediatric surgery, obstetrics, urology,					
thoracic surgery, orthopedic surgery (spine and joint operation), etc.					
Ethicon Endo-Surgery, Inc (America)					
A350525.01					
Ligasure Maryland					
curved shears, 23 cm shaft length					
Electrodes used for dissection and coagulation of human tissue and blood					
vessels during operation, which is connected to electric energy source					
Medtronic, Inc (USA)					
A35010.01					
Thunderbeat					
curved shears, 23 cm shaft length					
A device that can suture and incise tissue and blood vessels during surgery					
by using high frequency electrical output and ultrasonic vibration at the same					
time.					
Aomori Olympus Co.,Ltd					
Olympus Winter & Ibe GmBH					

1) Subject for trial mediation (surgical method, diagnosis method, etc.)

(1) Mediation subject and diagnosis method:

A case of primary gastric cancer diagnosed as pathologically adenocarcinoma through endoscopic biopsy,

[figure not shown]
(2) Mediation procedure:

- i. Under general anesthesia, insert 1 to 5 trocars around the navel and epigastrium and make a space with carbon dioxide. Laparoscopic distal gastrectomy and lymphadenectomy are performed using a randomly assigned energy-based shears.
- ii. Omentectomy: Partial resection
- **iii.** Gastric resection range: Perform a conventional distal gastrectomy to resect approximately 1/2 2/3 of the upper stomach.

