- (3) Patients who should undergo other long-term merger resection during distal gastrectomy. (except cholecystectomy)
- (4) Patients with significant ascites by CT.
- (5) Patients with cirrhosis in CT brfore surgery
- (6) Patients with heart disease (history of uncontrolled hypertension, angina or coronary artery disease, history of cardiac muscle disease, Ejection Fraction <50%)
- (7) Patients with inappropriate renal function (serum creatinine > 1.4 mg/dL or BUN > 26 mg/dL)
- (8) Patients with abnormal coagulation (PT INR > 1.2 or aPTT > 45 sec)
- (9) Uncontrolled diabetic patients
- (10) Inflammatory bowel disease patients including Crohn's disease, ulcerative colitis, tuberculous enteritis
- (11) Patients taking aspirin or platelet inhibitors within 5 days before surgery
- (12) Patients taking anticoagulants

- (13) Patients with the history of steroid use which needs stress dose inoculation
- (14) Pregnancy
- (15) Other patients who are deemed unable to participate in the clinical trial by the tester
- (16) History of sensitivity to iodine, in case the test using indocyanine green is applied
- (17) Previous history of gout

3) Target number of subjects and basis of calculation

Total target number: 189, competitive enrollment at SNUH and SNUBH Calculation methods of the subjects

Primary evaluation variable: Cerum CRP value on Post-op 2nd day **Subjects of the study**

Main analysis group

- A. Ultrasonic shears
- B. Bipolar sealing device

Explorative analysis group

C. Hybride device

Study hypothesis:

- Null hypothesis: No difference in CRP value on post-op 2nd day between two groups.
- Alternative hypothesis: Difference in CRP value on post-op 2nd day between two groups.

Hypothesis for calculation of number of subjects:

- (1) Level of significance, $\alpha = 0.05$
- (2) Ratio between groups, group A: group B = 1:1
- (3) Type 2 error (β) is 0.20, retaining power of the test at 80%
- (4) Ultrasound dissector and Bipolar's post-op's CRP average and standard deviation was 11.5 ± 6.6 and 8.0 ± 2.8 from preceding research of "Research of availability and safety in using Articulating bipolar vessel sealer system in early Robotic gastrectomy in early stage gastric cancer". Subjected patients were 17, small in numbers and it was for Robotic LAP surgery, not conventional LAP surgery. Therefore, to avoid chances for reflecting not enough subjected patients, we have calculated subjected patient numbers from conservative standard deviation.

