Program used for calculation: PASS (Power Analysis and sample size software; http://www.ncss.com)

Calculation result of study subject number:

Croup	Gro	up 1	Group 2		Subject	Total subject	
Group Comparison Me	Maan	Standard	Maan	Standard	number of	number with 10%	
Companson	Mean	deviation	Mean	deviation	each group	omission rate	
A vs B	11.5	6.6	8.0	6.6	57	189	

^{*} Total subject number with 10% omission rate = subject number of each group / 0.9 * 3

The primary concern of this study is to compare ultrasonic shears (A) and advanced bipolar Sealing device (B). Hybrid instrument (C) is expected to have similar temperature from its operating features even though there is no previous trustworthy research. We have decided total of 189 target patients, same numbers in A and B in order to contrast balance weigh in equal condition.

4) Study subjects invitation plan

Invitation will be made to patients, satisfying selection/exemption criteria among those who are gastric cancer patient visiting Gastric Cancer Center in Seoul National University Hospital or hospitalized gastric cancer patient who requested gastric cancer treatment to the study research team. Invitation will be explained verbally, with a consent form.

11. Research method

1) Research method in detail

Under general anesthesia of the patient, satisfying selection/exemption criteria, the subject will be appointed to the each study group of 1:1:1 ratio and the surgery will only use an energy-based device of each selected group. The patients will be randomized using web-based program, which will be generated by medical research collaboration center (MRCC), Seoul National University Hospital. Institutes and the presence of incision during anastomosis (intracorporeal or extracorporeal anastomosis) will be the stratification factors during randomization. Blood loss, blood transfusion volume, operation time, cytokines and others will be measured during the operation and amount of drainage, laboratory test and adverse reaction will be post-operatively observed and accessed. Unless follow-up or extension of admission is needed due to the adverse reaction, patients will be discharged during the post-op 5-10 days. Follow-up will be made until the first out-patient visit after 2-3 weeks of discharge.

(1) Evaluation criteria during operation

① Blood loss during operation: Output-input.

The blood loss will be measured with sum of absorbed blood in gauzes and absorbed amount using inhalator.

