A multivariable analysis of primary and primary secondary efficacy variables is performed. Multivariate analysis uses multiple linear regression models or multiple logistic regression models depending on the type of outcome variable. The main independent variable is the test, we will include the gender and stage of the stratified variables used in randomization in the model and the perturbed variables identified in the demographic and clinical history data analyzes to control the effect. For repeated measurement data, perform a multivariate analysis using the generalized estimation equation (GEE). If a significant interaction effect is found between the treatment group and the participating laboratories and / or the treatment group and the confounding variables, the effect is controlled by including the interaction term in the multivariate model.

• The content of the pre-planned subgroup analysis to be performed in this trial is as follows:

- Gender Male Female)
- BMI (<25 / ≥25)
- Cancer stage (TNM stage)
- Operator
- In vitro / Internal Anastomosis
- The differences between the groups were assessed using the Student's t-test (or the corresponding nonparametric Wilcoxon rank-sum test) or the χ2 test (or Fisher's exact test, the corresponding nonparametric method) Analysis. If control of disturbance variables is required, multivariate analysis is performed.

9-2) Treatment of missing values.

In general, the missing value will be treated as a missing state, and no alternative missing statistic is used. Therefore, only observations will be used for data analysis. Discrepancies data are replaced by missing values at the responsibility of the clinical trial manager.

10) Clinical trial and treatment standard

The same type of treatment and treatment will be given to patients with general gastric cancer who are being treated at Seoul National University Hospital.

11) Study Schedule

- 42 months after IRB approval: registration of clinical trial subjects and clinical trials
- 42 months ~ 48 months: Data analysis and presentation

12. Data and Safety Monitoring Plan

1) The person in charge of monitoring

- * Monitoring supervisor: [name], Associate Professor, Surgery, Seoul National University Hospital
- * Person in charge of monitoring: [name], Department of Nurse, Seoul National University Hospital

2) Data and safety information monitoring items

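### The primary CRP analysis allows a three-group ANOVA, although the trial's hypothesis and sample size concern only ultrasonic shears (A) versus the bipolar device (B)

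*Combined protocol and SAP*

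**What the plan says.** Section 10-3) (target number of subjects) puts A and B in the main analysis group and C in an exploratory one. It states a single hypothesis pair, with the null "Null hypothesis: No difference in CRP value on post-op 2nd day between two groups". The sample-size table has one row, A versus B, and the text below it says that this comparison is the study's main concern.

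Section 11, item 9)(1), the only sentence that names a test for the primary endpoint, reads "Student's t test or ANOVA test was performed by using the mean of CRP value on the second day between the three groups". It names no pair of arms and gives no rule for choosing between the two tests.

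On C, section 8-2) says "Hybrid device are expected to produce results similar to USA when considering the operating feature and heat generated" (the abbreviation stands for the ultrasonic shears), adds that "there is no previous study with hybrid device", and describes the comparison with C as exploratory.

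On covariates, section 9-1) says of the multivariable model for the primary variable that "we will include the gender and stage of the stratified variables used in randomization in the model". Sections 11-1) and 11-2) give the stratification factors as institute and intracorporeal or extracorporeal anastomosis.

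**The concern.** The two permitted tests answer different questions. The A-versus-B t test addresses the stated null. The ANOVA addresses A = B = C, so an arm that the protocol calls exploratory can decide the primary result. A significant ANOVA could be reported as the primary finding when A and B do not differ. A non-significant one could hide an A-versus-B difference that the t test would show. With the choice left open, a third risk is that whichever test comes out significant is the one reported.

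The main fault is the different null hypothesis. It is not a general loss of power, because in some configurations the ANOVA is the more powerful test.

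There is also a smaller, separate mismatch: the variables that section 9-1) calls randomisation strata are not the ones used to randomise.

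**Working it through.** **Inputs, all from section 10-3):** means 11.5 (A) and 8.0 (B), difference 3.5; SD 6.6 in both arms; two-sided 5% (the alternative has no direction); power 80%; 57 evaluable per arm; 189 in total (63 per arm) after a 10% allowance. The mean of C is not given, so it is varied below.

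**1. Reproducing the plan's figure.** Two-sample t test with noncentrality 3.5 / (6.6 × √(2/n)) on 2n − 2 degrees of freedom:
- n = 56: noncentrality 2.806, power 79.4%.
- n = 57: noncentrality 2.831, power 80.1%.
- n = 63: noncentrality 2.976, power 84.0%.

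The smallest n that reaches 80% is 57, as stated. The trial was therefore sized on a two-sided, two-group t test of A versus B. The total, 57 / 0.9 × 3 = 190, agrees with 189 apart from rounding.

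**2. The ANOVA when the stated null is true (A = B).** The noncentrality is λ = n × Σ(mean of arm − grand mean)² / SD². If only C differs, by d, the sum is (2/3)d². With n = 57, SD² = 43.56 and F on 2 and 168 degrees of freedom (critical value 3.050):

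| C differs by | λ | ANOVA rejects | A-versus-B t test rejects |
|---|---|---|---|
| 1 | 0.87 | 12.0% | 5% |
| 2 | 3.49 | 36.2% | 5% |
| 2.5 | 5.45 | 53.3% | 5% |
| 3.5 | 10.69 | 83.5% | 5% |

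With 63 per arm the last row becomes 87.2%.

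**3. The ANOVA at the design effect (A = 11.5, B = 8.0), n = 57.** The t test has 80.1% power whatever C is.

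| Mean of C | λ | ANOVA power |
|---|---|---|
| 8.0 or 11.5 | 10.69 | 83.5% |
| 8.5 or 11.0 | 9.38 | 78.1% |
| 9.75 (midway) | 8.01 | 71.0% |

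ANOVA power is below 80% only for C between about 8.3 and 11.2. With 63 per arm it is 87.2% at the ends and about 75.6% midway.

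**4. How often the two tests disagree** (400,000 simulated trials per scenario, normal data, n = 57). For C from 8.0 to 11.5 at the design effect, the decisions differ in about 11% to 12% of trials. At C = 11.5, only the ANOVA is significant in about 7.6% and only the t test in about 4.3%. At C = 9.75 the shares are about 1.3% and 10.4%. With 63 per arm, disagreement is about 10%.

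**5. Taking either test.** If A = B = C, claiming success when the t test or the ANOVA gives p < 0.05 has a type I error of about 7.5%, against the 5% in sections 10-3) and 9-1).

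**6. The strata.** Sections 11-1) and 11-2) agree on institute and anastomosis approach; section 9-1) names gender and stage. The documents do not say how much of the variation in CRP the real strata explain, so the effect of leaving them out of the model cannot be sized.

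**The case against.** The intent is reasonably clear. Section 10-3) points only to A versus B, and the one non-parametric fallback named in section 9-1), the Wilcoxon rank-sum test, is a two-sample test. The same t-test-or-ANOVA phrase recurs for most continuous secondary endpoints, so it may simply mean a t test for two groups and ANOVA for three. Section 8-2) expects C to resemble A. On that expectation, A = B implies A = B = C and the ANOVA rejects 5% of the time; at the design effect it has slightly more power than the t test. Finally, a SAP is promised before database lock.

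Much of this is fair. The intended comparison is not in doubt, the 83.5% false lead needs C to differ by the full design effect, and power is not the main issue. But intent does not withdraw the ANOVA that item 9)(1) allows. The two-groups-or-three reading is not applied consistently: for the ICG measurement the plan says "the mean value of the amount of ICG will be compared between each group using t test", with no ANOVA for three arms. Even on that reading, nothing says which result is primary. The closing t-test and Wilcoxon statement in section 9-1) follows the subgroup list and does not mention the primary endpoint. The expectation for C rests on no earlier study, by the protocol's own account. The promise of a SAP does not say that it will settle the test, and no such text is in the document supplied.

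**Conclusion.** The concern holds and should be fixed. The sample size is sound for A versus B; the fault is that the stated primary analysis allows a test of a different null hypothesis, with no rule for choosing. If A equals B, the ANOVA's rejection rate rises from 5% to 12.0%, 36.2% and 83.5% as C departs by 1, 2 and 3.5. At the design effect its power lies between 71.0% and 83.5% for C from 8.0 to 11.5, against a constant 80.1% for the t test. Free choice between the two gives about 7.5% type I error if all three arms are equal. These figures assume normal data, a common SD of 6.6 and 57 evaluable per arm, with C's mean varied by assumption. That the two tests have different nulls does not depend on any of these assumptions.

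The strata mismatch is minor. The plan does not rank its multivariable model against the test in item 9)(1); read as a supplement to that test, the error leaves the primary comparison valid.

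**What to change.** In section 11, item 9)(1), and in the SAP to be written before database lock, name one primary test: day 2 CRP, group A versus group B only, two-sided 5%. The t test on which the trial was sized is enough. A linear model on group, institute and anastomosis approach as entered at randomisation would match the stratified design and is a reasonable alternative, but one of the two must be fixed in advance. Label the three-group ANOVA and every comparison with C exploratory.

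In section 9-1), name institute and anastomosis approach as the randomisation strata; gender and stage may stay as additional covariates. Optionally, report the overall A-versus-B effect in that model from the fit without interactions, and show interactions as checks of heterogeneity.

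The cost is one sentence, one phrase and matching SAP text. Sample size and data collection do not change. C supports only exploratory statements, which is already its stated role. If the adjusted model is chosen, its result is slightly harder to present than two means.
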